The primary outcome for which the trial is powered is weight change from baseline to month 12. Differences in baseline characteristics in BE mHealth vs. mHealth participants will be examined using either t-test, Chi-Square tests or analysis of variance when appropriate. If baseline differences exist, they will be controlled for in outcome analyses. Distributional properties of continuously scaled variables will be examined to determine if normalizing transformations should be applied or if distributions other than normal should be used in the models. Pairwise contrasts among study groups using linear mixed effects models will be fitted by restricted maximum likelihood using REML as implemented in the PROC MIXED procedure or PROC GLIMMIX SAS 9.3 if residuals do not meet normality. Unconditional models will be fitted to assess for variability in participant intercepts and slopes, and determine whether these factors should be treated as random effects in conditional models. Unconditional models will also be used to evaluate whether the trajectory of the outcome is best characterized as linear / non-linear (quadratic and cubic). Estimated mean differences will be developed using linear contrasts and assessed with Wald statistics. These analyses will result in a detailed model of weight change across the 12-month trial. Within the linear mixed effects model, an a priori test of the difference between least squared means for treatment arms at the 12-month time point, adjusted for covariates, will test for between-arm differences at the 12-month assessment.

Missing data. Although concerted effort will be made to minimize missing data, we anticipate missing data due to refuted responses or lost to follow-up. Type of missingness will be evaluated and missing values will be imputed using full information or restricted maximum likelihood estimation^[100] depending on type of missing data, completely at random or just random missing data. All variables in our models will be used to impute missing data. Sensitivity analyses will be used to compare results with and without imputed values.

Inclusion/Exclusion Criteria:

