Participants will be 18-75 years of age, and have a BMI between 25-55kg/m². All sexes (male, female, non-binary) and racial/ethnic groups will be invited to participate. An upper age limit of 75 was chosen as individuals over 75 may have increased medical comorbidities and risks associated with unsupervised exercise. Obesity trials targeting adults from economically disadvantaged backgrounds have defined ‘economically disadvantaged’ as a household income of $\leq 300\%$ above the federal poverty level, which takes into account both income and household size.^[51] [9, 10, 52] This trial will do the same. During screening, participants will be asked to report their total household income and number of individuals in their household; those at or below 300% of the federal poverty line,^[51] or those qualifying for federal, state or local benefits (e.g., WIC, Husky Health, heat assistance, etc.) based on income, will be eligible. Participants will be required to have smartphones and use it daily for research purposes.

Individuals will be excluded if they: report being unable to walk 2 blocks without stopping; are currently participating in weight loss treatment, have a history of bariatric surgery, or lost $\geq 5\%$ in the past 6-months; have a current eating disorder; are pregnant or plan to become pregnant during the study period; report chest pain or loss of consciousness on the Physical Activity Readiness Questionnaire^[55]; have diabetes and are on insulin; are unable to read and write English; report a medical condition that could jeopardize their safety in a weight loss program with diet and exercise guidelines (e.g., planned/current pregnancy, cancer); or report conditions that, in the judgment of the PI, would render them unlikely to follow the protocol (e.g., relocation, dementia). During times of national emergency (e.g., COVID-19), participants without reliable internet (e.g., Wi-Fi or hardwired) or those unwilling to use their smartphone data plans will be excluded. If, during the study, a participant reports a medical condition (e.g., cancer, pregnancy) for which his/her doctor believes participation in the weight loss program is unsafe, the participant will be withdrawn from the weight loss intervention. The participant will, however, be asked to attend assessment visits for trial data completion.

Potential Harms/Risks and Inconveniences:

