participant and make a referral, if necessary. Another potential risk is that participants may not lose weight in the program. However, this is a potential risk in any weight loss program. Alternative treatments for overweight and obesity include diets with lower daily calorie recommendations, pharmacological interventions, and surgical procedures. These treatments are considered to have greater risks than the diet and activity program prescribed in this intervention. There is also a risk with using free WiFi networks when transmitting data. If smartphone settings have text notifications turned on (thus allowing people to see texts when the phone is locked), individuals around the participant may be able to see their text messages, reducing confidentiality re: study participation. If desired by participants, study staff will provide information on how to lock their phone and turn off locked-screen text message notifications such that the content of the text is not visible when the phone is locked. Locking the phone also mitigates risk of any phone data being obtained. It is also possible that participants may not lose weight or that they may lose weight and regain it. Finally, as noted in the protocol above, participants will be expected to spend time on intervention-related activities (e.g., meal preparation, physical activity, self-monitoring, platform use, visits); such time/effort is in service of participants' weight loss goals and participants can ultimately choose how much time/effort they wish to expend on such activities. To optimize your time during the study, research staff will help to ensure that all procedures and visits are conducted as efficiently as possible.

Assessment risks. Participants may become uncomfortable when completing assessment procedures; if this occurs, participants will be informed that they do not have to engage in any assessment procedures / answer any survey questions that are uncomfortable. Participants will also be expected to spend time on assessment-related activities; however, as noted above, assessments will be conducted as efficiently as possible and participants will be compensated for assessment completion.

Benefits:

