The proposed randomized controlled trial aims to examine the efficacy of a behavioral economics intervention for weight loss in adults from economically disadvantaged backgrounds. The intervention and measurement protocols pose minimal risk to participants. Consistent with NIH recommendations, because of this low risk status, the data safety monitoring (DSM) plan for this trial focuses on close monitoring by the principal investigator (PI) in conjunction with an external DSM Officer, along with prompt reporting of excessive adverse events and any serious adverse events to the IRB at the University of Connecticut, Office of Sponsored Programs, and, if necessary, the NIH.

The Project Coordinator will be responsible for assembling the data and producing DSM reports, as well as assuring that all parties (e.g., PI, Co-Is, Data and Safety Monitoring Officer, etc.) obtain copies of these reports. The injury/illness survey and adverse events form are attached to this document. Safety reports will be sent to the study statistician, the PI, Co-Is, and the Data Safety and Monitoring Officer.

Stopping Rules:

In this minimal risk intervention trial it is more likely that enrollment/randomization or retention issues may arise that could require stopping the trial, not excessive adverse events. However, as outlined elsewhere, we will monitor injury rates in all participants and the safety monitor, together with the study investigator, will alert the DSM Officer, IRB, and the NIDDK if a larger than reasonably expected injury rate should occur in any of the intervention conditions. Other issues related to stopping rules for this trial include:

New Information. It is exceedingly unlikely that any new information will become available during this trial that would necessitate stopping the trial.

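### Does the plan need a written rule for weights taken during or soon after pregnancy before they enter the month-12 comparison?

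*Combined protocol and SAP*

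**What the plan says.** The Inclusion/Exclusion Criteria exclude people who "are pregnant or plan to become pregnant during the study period". The same section then covers events after entry. If "a participant reports a medical condition (e.g., cancer, pregnancy) for which his/her doctor believes participation in the weight loss program is unsafe", she is withdrawn from the intervention. It adds: "The participant will, however, be asked to attend assessment visits for trial data completion". Under Assessment risks, "participants will be informed that they do not have to engage in any assessment procedures" that make them uncomfortable, so she may decline the weigh-in.

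The Data Analysis section defines the endpoint without qualification: "The primary outcome for which the trial is powered is weight change from baseline to month 12". The test is the between-arm difference in least-squares means at month 12 from a linear mixed model. The missing-data paragraph deals with absent values ("we anticipate missing data due to refuted responses or lost to follow-up"), and its one named sensitivity analysis is this: "Sensitivity analyses will be used to compare results with and without imputed values".

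No rule for weights affected by pregnancy appears there, in the weighing and quality-control text, or in the monitoring and stopping-rule sections. On recording of events, the Data Safety Monitoring section says "The injury/illness survey and adverse events form are attached to this document". Those forms are not in the text available for review, so whether they capture pregnancy and its dates is unknown.

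**The concern.** The protocol anticipates the event and arranges to go on collecting data after it, but does not say how the data are used. A likelihood-based mixed model takes every observed weight unless something removes it, so inclusion is the default. It is not a stated instruction.

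A weight late in pregnancy says little about response to a weight-loss program, and the protocol itself treats pregnancy as incompatible with entry. Withdrawal depends on the doctor's opinion, so a pregnant participant may also stay in treatment, and no analysis rule covers her weights either. Affected month-2 or month-6 weights would enter the fitted trajectory too.

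Two things would be at stake: extra variance in the primary comparison, and a decision about a few influential weights taken after the data have been seen. Distribution checks and data cleaning may flag an extreme value, but the plan does not say what happens next.

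**Working it through.** **Inputs from the documents.** Difference 2.5 kg, SD 5 kg, attrition 20%, 80 per arm for 88% power and 195 randomised (Justification of Sample Size); 1:1 allocation (Randomization); 5% type I error (Stopping Rules, Limits of Assumptions). A two-sided test is assumed.

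**Inputs not in the documents.** The number k of affected month-12 weights per arm (1 or 2) and the displacement d of each (5, 10 or 17 kg) are assumptions. The 17 kg end needs late pregnancy to coincide with month 12 and the participant to attend and be weighed.

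**Method.** Two-sample normal approximation at month 12: power = Φ(δ/SE − 1.96), with SE = SD × √(2/n). The documents give no within-person correlation, so the full mixed model cannot be computed.

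**Reproducing the plan's figure.** With n = 80, SE = 5 × √(2/80) = 0.79 kg and power is 88.5% (88.2% with the t distribution). The stated 88% stands. With the planned attrition, completers per arm are 195 × 0.8 / 2 = 78, SE = 5 × √(2/78) = 0.80 kg and power is 87.7%. This is the base case.

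**Weights kept, same number in each arm.** The arm variance becomes 25 + (k/78)(1 − k/78)d², and the expected difference does not change. For example, k = 1 and d = 10 gives 25 + (1/78)(77/78)(100) = 26.27, so the SD is 5.12 kg.

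| k per arm | d (kg) | SD (kg) | Power, weights kept | Power, set to missing | Gain (points) |
|---|---|---|---|---|---|
| 1 | 5 | 5.03 | 87.3% | 87.3% | 0 |
| 1 | 10 | 5.12 | 86.1% | 87.3% | 1.2 |
| 1 | 17 | 5.35 | 83.1% | 87.3% | 4.3 |
| 2 | 5 | 5.06 | 87.0% | 86.9% | 0 |
| 2 | 10 | 5.24 | 84.5% | 86.9% | 2.4 |
| 2 | 17 | 5.68 | 78.5% | 86.9% | 8.4 |

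The set-to-missing column uses n = 77 or 76 per arm with SD 5 kg. Gains are taken before rounding; at 5 kg they are slightly below zero, because losing the observation costs as much as the added noise.

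**Weights kept, two cases in one arm only.** The contrast moves by 2d/78, from 2 × 5/78 = 0.13 kg to 2 × 17/78 = 0.44 kg. The largest shift is 0.44/0.80, about half a standard error. It favours whichever arm has no cases, and nothing in the documents makes one direction more likely.

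**Can a form item still help?** The timeline puts Cohort 1 recruitment in summer 2021, shown in Year 2 Q4, and the end of all visits in Year 6 Q3. That is 15 quarters, or 3.75 years, later: about spring 2025. The protocol is dated December 17, 2025. If the schedule held, a new item for pregnancy dates would collect nothing prospectively.

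**The case for a change.** The best argument for a change is that a rule is cheap and removes discretion. One sentence and a data flag, fixed before the primary analysis, would prevent a choice made with the results in view. The month-12 visit carries the largest assessment payment ($100), so a withdrawn participant has a reason to attend and be weighed. An unlucky split can also matter. With two cases, both in BE mHealth, the numerator falls to 2.5 − 2d/78 and that arm's variance rises, giving power of 83.7%, 78.1% and 67.4% at 5, 10 and 17 kg.

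It is true that the plan is silent and that a written rule would be tidier. The rest carries less weight. The one-arm figures are conditional on a chance imbalance that could equally fall in mHealth, where it would enlarge the apparent effect; they do not describe a bias in the design. The material losses come from the top of an assumed range. Two per arm means four pregnant attendees among 156 completers, after planned pregnancy has been excluded, in a sample of all sexes aged 18 to 75. The documents support neither that count nor 17 kg in each case.

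Nor is the proposed rule clearly better. Setting weights to missing makes the model assume that these participants followed the course of others in their arm, although their treatment may have stopped. Using observed weights after treatment stops is a recognised approach, and it fits a protocol that keeps these visits for their data. Which analysis should be primary is a matter of judgement. A pregnancy-only rule would also leave open cancer, which the same sentence names and which may affect weight too.

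**Conclusion.** No change is called for. The plan leaves a detail unwritten, and analysts can fill it sensibly: they can identify the few affected weights from whatever was recorded and show the month-12 result with and without them. Followed as written, the plan keeps every observed weight, and the randomised comparison remains valid.

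For one or two cases per arm at 5 to 10 kg, the loss against the 87.7% base is about 0.4 to 3.2 points. The part recoverable by setting weights to missing is 0 to 2.4 points, bought with a missing-at-random assumption. Only 17 kg in every case raises the recoverable part to about 4 to 8 points. The stated 88% power is not in error.

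This rests on three assumptions: few pregnancies, because planned ones are excluded; no difference in their frequency by arm; and a simple month-12 comparison standing in for the mixed model. A record showing many affected weights, or a clear imbalance between arms, would reopen the question.

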Study Protocol

Title: Research Intervention to Support Health Eating and Exercise

NCT#: 04353258

Date: December 17, 2025

Clinical Trial/GCP Training

Is this a research study in which one or more human subjects are prospectively assigned¹ to one or more biomedical or behavioral interventions² (which may include placebo or other control) to evaluate the effects of those interventions on health-related biomedical or behavioral outcomes³ (i.e a clinical trial)? Indicate “yes,” “no,” or “N/A” in the space immediately below.

Yes.

Is the study fully or partially funded by the NIH? Indicate “yes,” “no,” or “N/A” in the space immediately below.

Yes.

Have the required key personnel completed Good Clinical Practice (GCP) Training? Indicate “yes,” “no,” or “N/A” in the space immediately below. (Note that IRB approval will not be given for NIH funded clinical trials until all required key personnel complete the GCP training.)

Yes.

For EACH Participant Population State the Number of Participants to be Enrolled and Screened and/or the number of participant records reviewed (including, HIPAA covered health records and FERPA covered school records), if applicable:

This study will include N=195 participants. Participants will be adults (ages 18-75) from all sex (male, female, non-binary) and racial/ethnic groups. They will also be from all education levels and have an income of <=300% of the federal poverty line or qualify for benefits (e.g., WIC, SNAP, etc.). Given that this is a weight loss study, participants will have a body mass index (BMI) in the overweight/obese range (25-55kg/m²). In order to meet our participant randomization goal, a total of 300 participants will need to be enrolled into the study / sign consent.

Justification of Sample Size:

The trial is powered for the primary aim: efficacy of BE mHealth vs. mHealth at month 12. We aim to detect a clinically meaningful difference of 2.5 kg between arms.[99] Based on previous trials with

¹The term “prospectively assigned” refers to a pre-defined process (e.g., randomization) specified in an approved protocol that stipulates the assignment of research subjects (individually or in clusters) to one or more arms (e.g., intervention, placebo, or other control) of a clinical trial.

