²An intervention is defined as a manipulation of the subject or subject’s environment for the purpose of modifying one or more health-related biomedical or behavioral processes and/or endpoints. Examples include: drugs/small molecules/compounds; biologics; devices; procedures (e.g., surgical techniques); delivery systems (e.g., telemedicine, face-to-face interviews); strategies to change health-related behavior (e.g., diet, cognitive/behavioral therapy, exercise, development of new habits); treatment strategies; prevention strategies; and, diagnostic strategies.

³ 3. Health-related biomedical or behavioral outcome is defined as the pre-specified goal(s) or condition(s) that reflect the effect of one or more interventions on human subjects’ biomedical or behavioral status or quality of life. Examples include: positive or negative changes to physiological or biological parameters (e.g., improvement of lung capacity, gene expression); positive or negative changes to psychological or neurodevelopmental parameters (e.g., mood management intervention for smokers; reading comprehension and /or information retention, behavioral intervention for psychiatric symptoms); positive or negative changes to disease processes; positive or negative changes to health-related behaviors; and, positive or negative changes to quality of life.

similar designs and our own trials, we expect a common within-group standard deviation of 5kg and a 20% attrition rate. [10-12] Hypothesis testing will be based on linear mixed effects models for longitudinal data, which increase power by fully exploiting the strong correlation in weight measures across time. Given these assumptions, if a total of N=160 participants (BE mHealth: N=80; mHealth: N=80) are enrolled, the trial will have 88% power to detect a statistically significant result. Accounting for attrition, 35 more participants will be added, so a total of 195 participants will be needed for this trial.

For EACH Participant Population Describe Screening Procedures, if applicable:

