Limits of Assumptions. It is possible that baseline differences between groups, excessive study dropouts, and/or missing data by the interim measurement time points will limit the value of data analysis of measurements at the post-treatment time point. Baseline differences will be evaluated after the first measurement time point and effects on the power to detect differences in the primary outcome will be examined and communicated to the PI, safety monitor, and NIDDK. Given the monitoring plans outlined elsewhere in this document, and the fact that this is a randomized trial, it is exceedingly unlikely that there will be baseline differences between groups of any magnitude to threaten the validity of the study.

Our retention rates have been historically excellent (e.g., >90%), however, excessive drop-outs could occur. In the grant proposal, we allowed for 20% dropout in the recruited numbers. With 20% dropout rate in all groups and 5% Type I error, the primary hypothesis is testable at 88% power. Dropout rates higher than 20% would be of concern, so we propose to monitor the dropout rate quarterly. Alert points are set at dropout rates of 20% (low alert), 30% (mid-alert), 35% (high alert), and 40% (extreme alert). With early alerts to problems, action would be taken to avoid higher level alerts; if a higher level alert should arise, more drastic remedial action would be invoked. To elucidate the implications arising when dropout rates reach various alerts, the following table estimates the power of the study for the primary hypotheses as the dropout rate increases above 20% (at which the study power is 88% for the primary hypothesis).

Dropout rate	20%	30%	35%	40%
Alert level	low	mid	high	extreme
Power available	88%	82%	76%	70%

The actions taken at each level of alert are given below:

- Mid-level alert = Conference call between study investigators to discuss approaches to minimize further losses to follow-up/dropouts.
- High-level alert = Conference call between investigators to determine further alterations of study protocol to complete the study with no further losses
- Extreme-level alert = In the unlikely event of a 40% dropout rate, study investigators would convene on a conference call to discuss the usefulness of continuing the study.

Participant Confidentiality:

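### The power figures at 35% and 40% dropout (76% and 70%) do not follow from the protocol's own inputs, which give about 80% and 76-77%

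*Combined protocol and SAP*

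**What the plan says.** Justification of Sample Size gives the design inputs: "We aim to detect a clinically meaningful difference of 2.5 kg between arms", and "we expect a common within-group standard deviation of 5kg and a 20% attrition rate". It states that if "a total of N=160 participants (BE mHealth: N=80; mHealth: N=80) are enrolled, the trial will have 88% power" to reach significance, and then: "Accounting for attrition, 35 more participants will be added, so a total of 195 participants will be needed for this trial". Allocation is 1:1 (Randomization).

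Stopping Rules, under Limits of Assumptions, repeats the anchor: "With 20% dropout rate in all groups and 5% Type I error, the primary hypothesis is testable at 88% power". It then sets four alert levels by dropout rate and says that "the following table estimates the power of the study for the primary hypotheses as the dropout rate increases above 20" percent. The table reads:

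| Dropout | 20% (low) | 30% (mid) | 35% (high) | 40% (extreme) |
|---|---|---|---|---|
| Power stated | 88% | 82% | 76% | 70% |

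No method is given for the table. The listed actions are conference calls. The one at the high alert concerns changes to the protocol; the one at the extreme alert is to "discuss the usefulness of continuing the study".

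**The concern.** The row falls in a way that loss of sample size alone does not produce. Stated power drops 6 points between 20% and 30% dropout, then another 6 points between 30% and 35%, which is half the step, and a further 6 between 35% and 40%. Power does fall somewhat faster as the sample shrinks, but not at twice the rate over this range.

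The table is there to tell the investigators what each alert means for the trial. If the last two figures are too low, they will overestimate the loss of power when they discuss altering the protocol or whether the study is still worth running. Stopping Rules itself regards enrolment or retention problems as a likelier reason to stop than adverse events.

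**Working it through.** **Inputs.** Difference 2.5 kg, SD 5 kg, 80 per arm for 88% power, 195 in total (Justification of Sample Size); 1:1 allocation (Randomization); 5% Type I error, with the dropout rate applying in all groups (Limits of Assumptions). Sidedness is not stated and is taken as two-sided.

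**Formula.** With n completers per arm, the noncentrality is λ = 2.5 / (5 × √(2/n)) = 0.5 × √(n/2). Under the normal approximation, power = Φ(λ − 1.960). The noncentral t was run alongside it.

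**Step 1: reproduce the plan's figure.** For n = 80, λ = 0.5 × √40 = 3.162 and power = Φ(1.202) = 88.5% (t: 88.2%). The stated 88% reproduces. A one-sided 5% test would give 93.5%, so two-sided is the reading that fits.

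**Step 2: recompute the row from 195**, with n = 195 × (1 − dropout) / 2.

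| Dropout | n per arm | λ | Power, normal | Power, t | Stated |
|---|---|---|---|---|---|
| 20% | 78.0 | 3.122 | 0.8775 | 0.8735 | 88% |
| 30% | 68.25 | 2.921 | 0.8317 | 0.8264 | 82% |
| 35% | 63.375 | 2.815 | 0.8036 | 0.7975 | 76% |
| 40% | 58.5 | 2.704 | 0.7716 | 0.7647 | 70% |

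The first two entries agree to within about 1 point. The last two are low by about 4 points and by 6-7 points.

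**Step 3: check the row against itself.** If only the number of completers changes, λ scales with the square root of the retained fraction, so N, SD and the difference are not needed.

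- From 88% at 20%: λ = 1.960 + 1.175 = 3.135. At 35%, 3.135 × √(0.65/0.80) = 2.826, power 80.7%. At 40%, 3.135 × √(0.60/0.80) = 2.715, power 77.5%. Any power that rounds to 88% (87.5-88.5%) gives 80.1-81.3% and 76.8-78.1%.
- From 82% at 30%: λ = 1.960 + 0.915 = 2.875. At 35%, 2.875 × √(0.65/0.70) = 2.771, power 79.1%. At 40%, 2.875 × √(0.60/0.70) = 2.662, power 75.9%. Any power that rounds to 82% (81.5-82.5%) gives 78.6-79.7% and 75.3-76.4%.

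Neither pair of ranges contains 76% at 35% or 70% at 40%.

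**Step 4: try other readings.**

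- Base of 200 (160/0.80), t: 88.2/83.6/80.8/77.5%. The last two entries still fail.
- Base of 160, t: 80.1/74.6/71.4/67.9%. This comes near 70% at 40%, but contradicts the stated 88% at 20%.
- One-sided 5%, anchored on 88% at 20%: 80.9-82.1% at 35% and 78.1-79.4% at 40%.
- All dropout in one arm, t: 74.5% at 30%, against 82% stated, and contrary to the text.

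**Step 5: what the stated figures would require.** From 195, power of 76% and 70% corresponds to about 41-42% and 48-49% dropout. To obtain them at 35% and 40% dropout, the SD would have to be about 5.2-5.3 kg and 5.4 kg, or the difference about 2.4 kg and 2.3 kg. The documents state none of these.

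**The case against.** The best counter-argument is that the figures are unexplained rather than wrong. The protocol says only that the table estimates power, and the analysis is a linear mixed model with no stated correlation. Measured from the 88% anchor, the 30% entry is also low: completer scaling gives 83.5% there (82.9-84.0% over the rounding range). All three entries above 20% dropout thus sit below the curve, by about 1.5, 5 and 7.5 points. That pattern would arise if power fell faster than the completer count, for instance because extra dropout dilutes the effect. Scaling λ by the retained fraction relative to 0.80, raised to a power of 0.75-0.8 instead of 0.5, gives roughly 88/80-81/76-77/70-71%, within about 2 points of the whole row.

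Part of this stands. The 30% entry is about 1 point low, and a correction should include it. The method is not stated, so an undisclosed assumption cannot be ruled out. But no dilution assumption appears in the documents. The exponent has to be chosen to fit, and it then misses the 30% entry by 1-2 points in the other direction. The mixed model does not help: a constant gain in precision is absorbed once the row is anchored at 88% (88.0/83.5/80.7/77.5%), and use of dropouts' earlier weights would, if anything, make power fall more slowly.

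It is also fair to say that the practical effect is small. No decision is tied to a power threshold.

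**Conclusion.** The concern holds, as a minor point. On the protocol's own inputs, power is about 80% at 35% dropout and 76-77% at 40%, so the table understates it by about 4 and 6-7 points. This rests on a two-sided 5% test, dropout equal across arms, and dropout affecting only the number of completers. The first two table entries and the headline 88% are consistent with those assumptions.

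The four stated powers do resemble dropout of 20/30/40/50% from 195 (87.4/82.6/76.5/68.6% by t; 87.8/83.2/77.2/69.5% by normal approximation), so a labelling slip is possible. That is inference only, and the conclusion does not depend on it.

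The error makes the trial look weaker than it would be. It moves no alert and leaves enrolment, Type I error and the primary analysis unchanged. Its only effect is on what the investigators are told when they discuss changing or continuing the study.

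**What to change.** Restate the power row from N = 195 as about 87-88%, 83%, 80% and 76-77% at 20%, 30%, 35% and 40% dropout, and add one sentence giving the method (two-sample comparison, 2.5 kg, SD 5 kg, two-sided 5%, equal dropout). Alternatively, keep 76% and 70% and state the additional assumptions that produce them. Leave the alert levels as they are. Optionally, note that 195 with 20% attrition leaves 195 × 0.80 = 156 completers (87-88% power), not 160.

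The cost is wording only: two entries change materially, the 30% entry moves by about 1 point, and one sentence is added. Enrolment, alert levels and the analysis stay as they are.
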